3.13.6 Visual Changes

Episodes of visual changes have been observed in subjects receiving trametinib, and ocular adverse events are known to be related to trametinib. An ophthalmologist should be consulted if changes in vision develop. However, if the visual changes are clearly unrelated to study treatment (e.g., allergic conjunctivitis), then monitor closely as it may be reasonable to defer ophthalmic examination. Special attention should be given to retinal findings (e.g., retinal pigment epithelial detachment (RPED) or retinovascular abnormalities (i.e., branch or central retinal vein occlusions (RVO)). For events of visual changes (regardless of severity) for which

an ophthalmic examination is conducted, a blood sample for PK analysis must be drawn as close as possible to the time of the event ([Section 7.1](#) for PK sample volume).

Guidelines regarding management and dose reduction for visual changes considered to be related to study treatment are provided in [Table 3-9](#).

Table 3-9 Mandatory dose modification and required clinical management for visual changes and/or ophthalmic examination findings

CTCAE v4.03 Grade*	Required adverse event management guidelines	Mandatory dose modification requirements
Grade 1	
 Consult ophthalmologist within 7 days of onset If visual changes are clearly unrelated to study treatment (e.g., allergic conjunctivitis), monitor closely but ophthalmic examination is not required. Report as SAE if RPED or RVO diagnosed 	
 If dilated fundus examination cannot be performed within 7 days of onset, interrupt trametinib until RPED and RVO can be excluded by retina specialist/ophthalmologist. On combination therapy dabrafenib may continue. If RPED and RVO excluded, continue (or restart) trametinib at same dose level If RPED suspected or diagnosed: see RPED dose modification Table 3-10 below If RVO diagnosed: Permanently discontinue trametinib (on combination therapy dabrafenib may continue)

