Grade 2 and Grade 3	
 Consult ophthalmologist immediately Report as SAE if RPED or RVO diagnosed 	
 Interrupt trametinib. On combination therapy, dabrafenib may be continued at the same dose. If RPED and RVO excluded, restart trametinib at same dose level If RPED diagnosed, see RPED dose modification Table 3-10 below If RVO diagnosed: Permanently discontinue trametinib (on combination therapy dabrafenib may continue) Permanently discontinue dabrafenib for \geq Grade 2 uveitis (including iritis and iridocyclitis) of > 6 weeks duration.
Grade 4	
 Consult ophthalmologist immediately Report as SAE if RPED or RVO diagnosed 	
 Interrupt trametinib. On combination therapy, dabrafenib may be continued at the same dose. If RPED and RVO excluded, may consider restarting trametinib at same or reduced dose If RPED or RVO diagnosed, permanently discontinue trametinib (on combination therapy dabrafenib may continue).

* Refers to NCI-CTCAE v4.03 'Eye disorders – Other, specify

Table 3-10 Mandatory dose modification and required clinical management for retinal pigment epithelial detachments (RPED)

CTCAE v4.03 Grade*	Required adverse event management guidelines	Mandatory dose modification requirements
Grade 1 RPED (Asymptomatic; clinical or diagnostic observations only)	
 If RPED worsens follow instructions below. 	Continue treatment with retinal evaluation monthly until resolution.

Grade 2-3 RPED (Symptomatic with mild to moderate decrease in visual acuity; limiting instrumental ADL)	
 • Retinal evaluation monthly. 	
 • Interrupt trametinib (on combination therapy dabrafenib may continue) 
If improved to \leq Grade 1, restart trametinib at lower dose (Appendix 2, dose reduction column)

---	---	---

* Refers to CTCAE Version 4.0 'Retinopathy'

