3.14 Dose Delay and Modification for Events Considered Related to Dabrafenib

General guidelines regarding management and dose reduction for adverse events that are considered by the investigator to be related to study treatment and for which specific guidelines do not apply are provided in [Table 3-6](#). These guidelines are intended primarily for toxicities not easily managed with routine supportive care. For example, alopecia is not an indication for dose modification, nor is grade 2 nausea and vomiting that can be easily managed with antiemetics.

These are general guidelines and investigators should always use clinical judgment in determining dose adjustments for any individual patient. Some toxicities may require hospitalization for stabilization, additional work-up, and consultation with a specialist before treatment can be restarted. Specific adverse events and recommended management include:

- **Palmar Plantar Erythrodysesthesia Syndrome (PPES)** – Measures for PPES should include:
 - Lifestyle modification: avoidance of hot water, traumatic activity, constrictive footwear, or excessive friction on the skin and the use of thick cotton socks and gloves, and shoes with padded insoles
 - Symptomatic treatments: apply moisturizing creams frequently, topical keratolytics (e.g. urea 20-40 % cream, salicylic acid 6%, tazarotene 0.1% cream, fluorouracil 5% cream), clobetasol propionate 0.05% ointment for erythematous areas, topical lidocaine 2%, and / or systemic pain medication such as nonsteroidal anti-inflammatory drugs, codeine, and pregabalin for pain.

Dose modification may also be required (See [Section 3.15](#)).

- **Pancreatitis** – In the event of abdominal pain or suspected pancreatitis, amylase and lipase laboratory samples should be collected for confirmation of the diagnosis. Patients should be closely monitored when re-starting dabrafenib after an episode of pancreatitis.
- **Uveitis** - Treatment with dabrafenib has been associated with the development of uveitis, including iritis. Monitor patients for visual signs and symptoms (such as, change in vision, photophobia and eye pain) during therapy. Permanently discontinue dabrafenib for persistent \geq grade 2 uveitis (including iritis and iridocyclitis) of $>$ 6 week duration. No dose modification of trametinib is required when taken in combination with dabrafenib. See [Section 3.13.5](#).

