3.15 Guidelines for Dose Modifications and Toxicity Management for Combination Therapy

If treatment related toxicities occur when dabrafenib is used in combination with trametinib then both treatments should be simultaneously dose reduced, interrupted or discontinued with the exception shown below:

- Dose modification is necessary for only dabrafenib
 - Mild to moderate pyrexia ([Section 3.15.1](#))
 - Uveitis ([Section 3.13.5](#) and [Section 3.14](#))
- Dose modifications are necessary for only trametinib:
 - Retinal vein occlusions (RVO) and retinal pigment epithelial detachment (RPED) ([Section 3.13.5](#))
 - Left ventricular ejection fraction (LVEF) reduction (asymptomatic, [Section 3.12.3.1](#))
 - Pneumonitis and interstitial lung disease (ILD) (grade 4, [Section 3.13.7](#))

The severity of adverse events (AEs) will be graded utilizing the NCI-CTCAE v4.03 ([NCI 2009](#)). Guidelines for dose modifications and interruptions for management of common toxicities associated with dabrafenib are provided in this section.

Trametinib dose reduction for patients enrolled in all parts of the study should follow dose reduction column in the trametinib dosing nomogram in Appendix 2.

Dabrafenib dose reduction should follow the dose reduction column in the dabrafenib dosing nomogram in Appendix 2 provided for patients enrolled in Part C and Part D, as described below

- Dabrafenib dose modification levels in Part C
 - If a subject is dosed at Dose Level 1, and requires dose reduction, treatment must be discontinued
 - If a subject is dosed at Dose Level 2, and requires dose reduction, follow the dose reduction column in dosing nomogram
- Dabrafenib dose modification levels in Part D.
 - Follow dose reduction column in dosing nomogram

Nomograms for each dosing level are provided in [Appendix 2](#).

If a second dose reduction is required, the treatment should be discontinued.

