6.3 Permanent Discontinuation from Study Treatment

Subjects will receive study treatment until disease progression, death or unacceptable toxicity, including meeting stopping criteria for liver chemistry defined in [Section 3.12.1](#). In addition, study treatment may be permanently discontinued for any of the following reasons:

- serious deviation(s) from the protocol that result in a significant risk to the patient's safety;
- subject becomes pregnant;
- request of the subject or proxy (withdrawal of consent by subject or proxy);
- investigator's discretion;
- a dose delay due to study treatment related toxicity of $>$ 28 days;
- intercurrent illness that prevents further administration of study treatment(s);
- subject is lost to follow-up;
- sponsor terminates the study.

The primary reason study treatment was permanently discontinued must be documented in the subject's medical records and eCRF.

If the subject voluntarily discontinues from treatment due to toxicity, 'AE' will be recorded as the primary reason for permanent discontinuation on the eCRF.

Once a subject has permanently discontinued from study treatment, the subject will not be allowed to be retreated. All subjects who discontinue from study treatment will have safety assessments at the time of discontinuation and during post-study treatment follow-up as specified in Time and Events Table (see [Section 7.1](#)).

Adverse Events must be followed for a minimum of 30 days after the last dose. If it is not practical for the subject to return to the clinic, this data may be collected via telephone from the parent/caregiver/subject (as appropriate).

The discontinuation related safety assessments (same assessments as Final visit in the Time and Events Table) may be completed at any time from the last dose to 30 days after the last dose. Ongoing toxicities should be followed to resolution if at all possible. If the decision to discontinue the patient occurs at a regularly scheduled visit, that visit may become the EOT visit rather than having the patient return for an additional visit.

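### For uveitis on combination therapy, Table 3-9 interrupts trametinib at Grades 2 to 4 without exempting diagnosed uveitis, while Sections 3.14 and 3.15 leave trametinib unmodified; the gap is temporary at Grades 2-3 and wider at Grade 4

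*Protocol*

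**What the plan says.** Table 3-9 in Section 3.13.6 is titled "Mandatory dose modification and required clinical management for visual changes and/or ophthalmic examination findings". For Grade 2-3, and again for Grade 4, its dose-modification column opens with "Interrupt trametinib. On combination therapy, dabrafenib may be continued at the same dose".

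The two rows then differ. The Grade 2-3 row continues "If RPED and RVO excluded, restart trametinib at same dose level", and it ends by requiring permanent discontinuation of dabrafenib for Grade 2 or higher "uveitis (including iritis and iridocyclitis) of > 6 weeks duration". The Grade 4 row says "If RPED and RVO excluded, may consider restarting trametinib at same or reduced dose" and has no uveitis line.

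Section 3.14, under uveitis, gives the same over-6-week dabrafenib discontinuation for Grade 2 or higher, with no upper grade limit, and adds "No dose modification of trametinib is required when taken in combination with dabrafenib".

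Section 3.15 makes joint modification of both drugs the default and then lists exceptions. Uveitis stands under "Dose modification is necessary for only dabrafenib". RVO and RPED stand on a separate trametinib-only list.

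**The concern.** A child on both drugs who has diagnosed uveitis of Grade 2 or higher falls under three instructions that do not agree about trametinib. The mandatory table interrupts it. The two sections on dabrafenib-related and combination toxicity say it is left alone. The protocol does not say which text takes precedence, and the cross-references meant to connect them lead to the wrong section.

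This matters for the data as well as for conduct. Section 3.9.4 makes safety and tolerability primary endpoints in Parts C and D. If sites follow different sections, a recorded trametinib interruption or reduction for uveitis may reflect the page consulted rather than tolerance of trametinib. Section 3.13 allows at most one trametinib dose reduction, so a reduction taken through the Grade 4 row would use that allowance for an event where 3.14 requires no trametinib change.

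**Working it through.** The plan gives no figure to reproduce here, so the check sets the passages side by side for a subject on both drugs.

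**Does Table 3-9 cover uveitis?** Yes. Its title extends to findings on eye examination, and its Grade 2-3 cell names uveitis, iritis and iridocyclitis. Nothing in the cell exempts these from its opening instruction.

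**Grade 2-3, at onset**
- Table 3-9: trametinib interrupted; dabrafenib may continue.
- 3.14: no trametinib modification required.
- 3.15: only dabrafenib modified.
- Result: conflict on trametinib.

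**Grade 2-3, after RPED and RVO are excluded**
- Table 3-9: trametinib restarts at the same dose; dabrafenib stops permanently if uveitis lasts more than 6 weeks.
- 3.14: same dabrafenib stop; trametinib unmodified.
- Result: 3.14 and the table agree from this point. The Grade 2-3 conflict is a temporary trametinib interruption.

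**Grade 4**
- Table 3-9: trametinib interrupted. Even with RPED and RVO excluded, restart is only an option, at the same or a reduced dose. Dabrafenib may continue, and no duration limit is printed in this row.
- 3.14: no trametinib modification required; dabrafenib stops for persistent uveitis beyond 6 weeks at any grade from 2 upward.
- Result: conflict on trametinib that can outlast the diagnostic work-up, and a missing dabrafenib line.

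**Dabrafenib before 6 weeks**
- 3.15 calls a dabrafenib modification necessary.
- Table 3-9 permits continuation at the same dose.
- 3.14 gives only the discontinuation after 6 weeks. It reserves the general Table 3-6 for events without specific guidance.
- Result: no section specifies the modification that 3.15 calls necessary.

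**Cross-references.** Sections 3.14 and 3.15 both refer the reader to 3.13.5 for uveitis. So do Section 1.7.2 for ocular effects and the list in Section 3.13 for visual changes. Section 3.13.5 is Hypertension; Visual Changes is 3.13.6.

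**Subjects to whom the rule applies**
- Planned (Section 5.1): 24 in Part C + 30 in Part D = 54.
- Enrolled by 17 July 2020 (Amendment 9 rationale): 18 + 30 = 48.

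**The case against.** The best defence is that Table 3-9 deals with an eye event whose cause is not yet known. Section 3.13.6 asks for special attention to retinal findings, and the Grade 2-3 row holds trametinib only until RPED and RVO are excluded. Sections 3.14 and 3.15 would then apply once uveitis is diagnosed. This reading accounts for most of the Grade 2-3 discrepancy, and to that extent it stands. It does not remove the discrepancy: the row names uveitis without exempting an already diagnosed case from the hold, and no text says that 3.14 overrides a mandatory table. Nor does it explain Grade 4, where trametinib may stay off or be reduced after the retinal causes have been excluded.

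On dabrafenib at Grade 4, the defence is partly right. The row is permissive, so stopping after 6 weeks under 3.14 breaches nothing in it. The missing line is an omission, not a contrary order.

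A reader might infer two stronger points that the documents do not support:

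- **That the held drug switches from trametinib to dabrafenib depending on the section, so that handling is opposite.** No section orders a dabrafenib hold for uveitis before 6 weeks, and 3.15 names no interruption. The direct disagreement is whether trametinib is interrupted.
- **That the Section 6.3 criterion, "a dose delay due to study treatment related toxicity of $>$ 28 days", pre-empts the 6-week rule.** This needs a dabrafenib hold that the protocol never instructs. Section 6.3 says treatment may be discontinued for that reason, and the two limits measure different things: length of a dose delay and length of uveitis.

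**Conclusion.** The inconsistency is real and stands in the current text. At Grades 2-3 it is confined to a temporary trametinib interruption. At Grade 4 it is larger: trametinib restart is discretionary and may be at a reduced dose, and the over-6-week dabrafenib statement is absent. The unspecified dabrafenib modification in 3.15 and the wrong section references add to it.

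The instructions apply to combination subjects, 54 planned and 48 enrolled. That is the population under the rule, not the number affected: the protocol text at hand gives no uveitis incidence for the study, and none is assumed. All cohorts are closed to enrolment. The practical reach is therefore subjects still on combination treatment and the interpretation of trametinib interruptions and reductions already recorded. The conclusion rests on reading Table 3-9 as covering uveitis, which its title and its Grade 2-3 row support. It takes no position on which handling is clinically right. The correction should be made, but nothing here invalidates the design.

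**What to change.** Reconcile Table 3-9, Section 3.14 and Section 3.15 so that one rule states, separately for Grades 2, 3 and 4, how each drug is handled for uveitis on combination therapy. That rule should say:

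- whether the initial trametinib step applies once uveitis is diagnosed;
- which grades the over-6-week dabrafenib statement covers, with the line appearing in each row it is meant to cover;
- what dabrafenib modification, if any, Section 3.15 refers to before 6 weeks.

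The clinical content is for the sponsor to decide. The other two places should then refer to that single rule. Correct the references to 3.13.5 in Sections 3.14 and 3.15 for uveitis, and in 1.7.2 and 3.13 for ocular effects and visual changes, so that they point to 3.13.6.

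The cost is amendment wording in a few places, with no added procedures, visits or subjects. When trametinib interruptions and reductions for uveitis are reported in Parts C and D, it would help to note that the instructions differed between sections.

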3.13.7 Pneumonitis

Pneumonitis has been observed in subjects receiving trametinib. To reduce the risk of pneumonitis, subjects will be monitored closely for symptoms, evaluated with imaging and functional tests if clinically indicated. Dose modification and supportive care guidelines for pneumonitis are described in [Table 3-11](#).

Table 3-11 Mandatory dose modifications and recommended clinical management guidelines for pneumonitis

CTCAE v4.03 Grade	Recommended adverse event management guidelines	Mandatory dose modification requirements
Grade 1	
 • CT scan (high-resolution with lung windows) • Clinical evaluation and laboratory work-up for infection • Monitoring of oxygenation via pulse-oximetry • Consultation with pulmonologist 	
 • Continue study treatment (s) at current dose
Grade 2	
 • CT scan (high-resolution with lung windows) • Clinical evaluation and laboratory work-up for infection • Consult pulmonologist • If feasible, pulmonary function tests -if <normal, repeat every 8 weeks until \geqnormal • Bronchoscopy with biopsy and/or BAL • Symptomatic therapy including corticosteroids if clinically indicated 	
 • Interrupt trametinib until recovery to grade \leq1 (on combination therapy, dabrafenib may continue) • Restart treatment with reduced trametinib dose level (Appendix 2, dose reduction column) • Escalation to previous dose level after 4 weeks if a period of 4 weeks of treatment have passed since restarting dosing at the lower dose level and there is no recurrence of the AE • If no recovery to grade \leq1 within 4 weeks, permanently discontinue trametinib (on combination therapy, dabrafenib may continue)
Grade 3	
 • CT scan (high-resolution with lung windows) • Clinical evaluation and laboratory work-up for infection • Consult pulmonologist • If feasible, pulmonary function tests-if <normal, repeat every 8 weeks until \geqnormal • Bronchoscopy with biopsy and/or BAL if possible • Symptomatic therapy including corticosteroids as clinically indicated 	
 • Interrupt trametinib until recovery to grade \leq1 (on combination therapy, dabrafenib may continue) • When recovered to grade \leq1, treatment with trametinib may be restarted at reduced dose (Appendix 2, dose reduction column) • If no recovery to grade \leq1 within 4 weeks, permanently discontinue trametinib (on combination therapy, dabrafenib may continue)
Grade 4	
 • Same as grade 3 	
 • Permanently discontinue trametinib (on combination therapy, dabrafenib may continue)

Abbreviations: BAL= bronchioalveolar lavage; CT = computed tomography; CTCAE = Common Terminology Criteria for Adverse Events
		

3.14 Dose Delay and Modification for Events Considered Related to Dabrafenib

General guidelines regarding management and dose reduction for adverse events that are considered by the investigator to be related to study treatment and for which specific guidelines do not apply are provided in [Table 3-6](#). These guidelines are intended primarily for toxicities not easily managed with routine supportive care. For example, alopecia is not an indication for dose modification, nor is grade 2 nausea and vomiting that can be easily managed with antiemetics.

These are general guidelines and investigators should always use clinical judgment in determining dose adjustments for any individual patient. Some toxicities may require hospitalization for stabilization, additional work-up, and consultation with a specialist before treatment can be restarted. Specific adverse events and recommended management include:

- **Palmar Plantar Erythrodysesthesia Syndrome (PPES)** – Measures for PPES should include:
 - Lifestyle modification: avoidance of hot water, traumatic activity, constrictive footwear, or excessive friction on the skin and the use of thick cotton socks and gloves, and shoes with padded insoles
 - Symptomatic treatments: apply moisturizing creams frequently, topical keratolytics (e.g. urea 20-40 % cream, salicylic acid 6%, tazarotene 0.1% cream, fluorouracil 5% cream), clobetasol propionate 0.05% ointment for erythematous areas, topical lidocaine 2%, and / or systemic pain medication such as nonsteroidal anti-inflammatory drugs, codeine, and pregabalin for pain.

Dose modification may also be required (See [Section 3.15](#)).

- **Pancreatitis** – In the event of abdominal pain or suspected pancreatitis, amylase and lipase laboratory samples should be collected for confirmation of the diagnosis. Patients should be closely monitored when re-starting dabrafenib after an episode of pancreatitis.
- **Uveitis** - Treatment with dabrafenib has been associated with the development of uveitis, including iritis. Monitor patients for visual signs and symptoms (such as, change in vision, photophobia and eye pain) during therapy. Permanently discontinue dabrafenib for persistent \geq grade 2 uveitis (including iritis and iridocyclitis) of $>$ 6 week duration. No dose modification of trametinib is required when taken in combination with dabrafenib. See [Section 3.13.5](#).
- **Hyperglycemia** - Hyperglycemia requiring an increase in the dose of, or initiation of insulin or oral therapy can occur with dabrafenib. Monitor serum glucose levels as clinically appropriate during treatment with dabrafenib in subjects with pre-existing diabetes or hyperglycemia. Advise patients to report symptoms of severe hyperglycemia such as excessive thirst or any increase in the volume or frequency of urination.

Investigators should always err on the side of caution in these settings if treatment-related toxicity is a possibility.

Please refer to [Table 3-6](#) for general dose modification guidelines for trametinib and dabrafenib.

When an individual's adverse reactions are under effective management, dose re-escalation following the same dosing steps as de-escalation may be considered. The dabrafenib dose should not exceed 150 mg twice daily.

